#### 12.1 Power calculation

Estimated treatment effect size and retention to guide the required number of participants for NEAT was based on best available trial evidence and meta-analysis. The trial is designed to compare the effectiveness of extended-release naltrexone (XR-NTX) and oral tablet naltrexone (O-NTX) on an intention-to-treat basis at 12 weeks post-randomisation. There are two comparisons: XR-NTX vs. placebo, and XR-NTX vs. O-NTX. Based on a 2007 HTA systematic review and the naltrexone depot trial by [name] and her colleagues in the USA, the following assumptions were made:

- A. The mean percentage of heroin-free urine drug screens at 12 weeks post-randomisation will be approximately 0.30 (30%) in the placebo and O-NTX treatment arms, respectively, and 0.55 (55%) in the XR-NTX treatment 
- B. The standard deviations of the treatment groups will be of a similar magnitude We estimate the common standard deviation to be 30.
- C. The minimal clinically significant difference between the XR-NTX and O-NTX / placebo group will be a 25 point difference in percentage observable at 12 weeks post-randomisation, equating to an effect size of 0.8.
- D. An expected 40% attrition rate based on previous trial data.
- E. To control for multiple comparisons in the primary analyses, Bonferroni correction has been applied to the significance level reducing it by a factor 2. Thus the significance level will be considered at 2.5%.

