## 12.2 Estimated required sample size

With an anticipated 0.8 effect size, a common standard deviation of 30, expected attrition at 40%, and testing significance at 2.5%, a sample size of 300 participants randomized on a 1:1:1 basis to the three arms (100 participants in each arm) will have 98% power to detect a 25 point difference in the percentage heroin-negative urines for the planned comparisons of active treatment arm XR-NTX vs. placebo and active treatment arm XR-NTX vs. standard oral treatment O-NTX.

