## 12.4 Analysis

A comprehensive statistical analysis plan will be be developed and agreed with the trial's oversight committees.

There will be no planned interim analyses. An analysis of the data will be conducted once the trial database has closed. The Data Monitoring Committee will collate effectiveness and safety data during the trial to inform their recommendations to the Trial Steering Committee. A mid-trial formal data analysis is not envisaged.

Statistical analysis will be by intention-to-treat. Descriptive analyses (Q-Q plots, means and standard deviation, median and IQR, or numbers and proportions as appropriate) will be performed for the baseline variables and outcome variables, and will be described by treatment group. The time-to-event outcomes will be explored using life tables and survival plots (Kaplan-Meier curves).

The primary outcome analysis for the effectiveness of XR-NTX vs. placebo, and XR-NTX vs. O-NTX is described in Section 9.1. The secondary outcome analyses are described in Section 9.2.

In the case of missing assessments, such analysis can include these participants provided that prerandomisation values are available for the respective scales. The analysis presumes that the drop-out mechanism is missing at random (MAR). We will examine the scope for using multiple imputation (MI) to generate complete data records as a means of achieving greater efficiency and reduced missing data bias. We will also include as covariates in both model and MI any variables found to be associated with drop-out.

The significance level will be 2.5% (two-sided) for the primary outcome analysis and 5% (two-sided) for secondary outcome analysis. Group difference estimates and associated confidence intervals will be reported. The trial statistician will remain blind whenever possible until the main analyses have been completed.

Loss to follow-up, departures from randomized treatment and the prevalence of serious adverse events will be reported at 12, 16, 24 and 36 weeks post randomization.

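### The two primary contrasts are both held at 2.5% by a fixed Bonferroni split; Holm's step-down keeps the same 5% familywise bound and never rejects less (an efficiency point, not an error)

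*Protocol*

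**What the plan says.** Protocol section 12.1 names the primary contrasts: "There are two comparisons: XR-NTX vs. placebo, and XR-NTX vs. O-NTX". Item E of that section deals with multiplicity: "Bonferroni correction has been applied to the significance level reducing it by a factor 2". Section 12.2 uses the resulting 2.5% level for the sample size, and section 12.4 carries it into the analysis: "The significance level will be 2.5% (two-sided) for the primary outcome analysis". The three sections agree with each other. None of them lets the level for one contrast depend on the result of the other.

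The power statement in section 12.2 is that 300 participants, 100 per arm, "will have 98% power to detect a 25 point difference in the percentage heroin-negative urines for the planned comparisons".

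**The concern.** Under a fixed split, the 2.5% spent on a contrast that has been rejected is not used again. Suppose XR-NTX beats placebo at p = 0.001 and beats O-NTX at p = 0.03. The plan must call the second result non-significant. Holm's procedure would compare 0.03 with 5% and reject, and the chance of at least one false rejection would still be at most 5%.

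The loss falls on whichever contrast has the larger p-value. Section 6.2.1 lists superiority over placebo (A) and over O-NTX (B) as separate primary questions, so power for the second of them is worth having if it costs nothing in type I error. The choice is made in the protocol itself and is not left to the statistical analysis plan.

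**Working it through.** **Inputs from the protocol (sections 12.1, 12.2 and 12.4)**
- Difference: "a 25 point difference in percentage observable at 12 weeks post-randomisation, equating to an effect size of 0.8".
- SD: "We estimate the common standard deviation to be 30". Then 25/30 = 0.833, so 0.8 is a rounding; both values are carried below.
- Loss: "An expected 40% attrition rate based on previous trial data". Analysed per arm: 100 × (1 − 0.40) = 60.
- Level: 2.5% two-sided per contrast, critical value 2.241. The 5% two-sided critical value is 1.960.

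**Derived, not stated:** with equal arms and a shared XR-NTX arm, the two test statistics have correlation 0.5.

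**Step 1. Reproduce the 98%.** Expected z = d × √(n/2); power = Φ(expected z − 2.241).
- d = 0.8: 0.8 × √30 = 4.382; Φ(2.141) = 98.4% (noncentral t: 98.2%).
- d = 0.833: 0.833 × √30 = 4.564; Φ(2.323) = 99.0% (noncentral t: 98.9%).

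The stated figure reproduces as power for one contrast.

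**Step 2. Power to establish both contrasts.** With Z1 and Z2 bivariate normal, correlation 0.5:
- Bonferroni: P(Z1 > 2.241 and Z2 > 2.241).
- Holm: P(larger Z > 2.241 and smaller Z > 1.960).

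| True difference vs. placebo / vs. O-NTX | Analysed per arm | Bonferroni | Holm |
|---|---|---|---|
| d = 0.8 / 0.8 (design) | 60 | 97.0% | 98.5% |
| 25 / 25 points, SD 30 (design) | 60 | 98.1% | 99.1% |
| 25 / 15 points (assumed) | 60 | 68.9% | 78.0% |
| d = 0.8 / 0.8, reduced accrual (assumed) | about 42 | 86.4% | 91.7% |
| 25 / 25 points, no loss (assumed) | 100 | over 99.9% | over 99.9% |

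The reduced-accrual row uses the rates in section 24: 2 centres × 1 per week × 104 weeks = 208 recruited; 208/3 = 69.3 per arm; 69.3 × 0.60 = 41.6 analysed per arm.

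In the 25 / 15 row almost all of the gain is in the weaker contrast. Power for XR-NTX vs. O-NTX taken alone goes from 69.1% to 78.1%.

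**Step 3. Familywise error (2 million simulated draws).**
- Both nulls true: 4.65% under either method.
- One null true, the other contrast at the design effect: 2.5% under Bonferroni, 4.9% under Holm.

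Neither exceeds 5%. The two methods share the same bound, but Holm uses more of it when only one null is true.

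**The case against.** The case for leaving the text alone is strong. Bonferroni is valid, prespecified and stated consistently, and choosing one valid procedure over another is the designers' decision. At the design effect, joint power is already 97–98%, so the gain is 1.0 to 1.5 points. If all 100 per arm enter the primary analysis, as section 9.1 may imply by its intention-to-treat sample and its mention of scoring missed samples as positive, the gain at d = 0.8 almost vanishes. The larger gains rest on chosen scenarios. A 15-point difference is below what section 12.1 takes as the smallest clinically important one, and the accrual shortfall is a separate matter that Holm does not repair. Bonferroni also has matching 97.5% intervals, and section 12.4 promises confidence intervals. Finally, section 25 records that the trial was wound down with six participants, so the change has value only for a later design. All of this stands and limits the weight of the point. It does not remove it, because Holm asks for no extra patients, assumptions or error rate.

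A reader might infer that the trial must win both contrasts to succeed, and that the fixed split therefore threatens its main conclusion. The protocol does not say so: objectives A and B are separate questions, each answered by its own contrast. If winning both were the sole criterion, each could be tested at 5% with no adjustment, and Holm would not be the remedy. The argument is only about power for whichever contrast is tested second; the both-contrasts figure is a summary of that.

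**Conclusion.** The point holds as a low-priority improvement. Sections 12.1 and 12.4 fix a procedure that is correct but uniformly no more powerful than a simple alternative with the same 5% bound. Under the protocol's own assumptions, the power to establish both contrasts would rise from 97.0–98.1% to 98.5–99.1%. Gains of about 5 to 9 points appear only under the assumed departures shown: accrual at the section 24 rate, or a smaller true advantage over O-NTX than over placebo.

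These figures assume normally distributed test statistics, equal arm sizes, a common SD and, in the main case, 60 analysed per arm. They do not show that the trial is underpowered, that its type I error is wrong or that the 98% is misstated.

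**What to change.** In section 12.1 item E and section 12.4, replace fixed testing at 2.5% with Holm's procedure at a familywise two-sided 5%: test the smaller of the two p-values at 2.5% and, only if it is significant, test the other at 5%.

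Leave the sample size and the 98% in section 12.2 as they are. The 98% remains correct as power per contrast at 2.5%, and Holm can only add to it. State that 97.5% confidence intervals will be reported for both contrasts.

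The cost is one or two sentences and no patients. The small downside should be stated in the same place: the contrast tested second may be significant under Holm while its 97.5% interval includes zero. A team that puts agreement between test and interval first could reasonably keep Bonferroni for that reason.

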## 12.2 Estimated required sample size

With an anticipated 0.8 effect size, a common standard deviation of 30, expected attrition at 40%, and testing significance at 2.5%, a sample size of 300 participants randomized on a 1:1:1 basis to the three arms (100 participants in each arm) will have 98% power to detect a 25 point difference in the percentage heroin-negative urines for the planned comparisons of active treatment arm XR-NTX vs. placebo and active treatment arm XR-NTX vs. standard oral treatment O-NTX.

#### 12.3 Randomisation

The King's Clinical Trials Unit will oversee randomization. Recruiting centre research staff will randomize participants to one of the three arms of the study (ratio 1:1:1), stratifying by clinical centre, prison or community referral, and recent cocaine use (yes or no) using randomly varying block sizes, via the online randomization system based at King's CTU.

## 12.4 Analysis

A comprehensive statistical analysis plan will be be developed and agreed with the trial's oversight committees.

There will be no planned interim analyses. An analysis of the data will be conducted once the trial database has closed. The Data Monitoring Committee will collate effectiveness and safety data during the trial to inform their recommendations to the Trial Steering Committee. A mid-trial formal data analysis is not envisaged.

Statistical analysis will be by intention-to-treat. Descriptive analyses (Q-Q plots, means and standard deviation, median and IQR, or numbers and proportions as appropriate) will be performed for the baseline variables and outcome variables, and will be described by treatment group. The time-to-event outcomes will be explored using life tables and survival plots (Kaplan-Meier curves).

The primary outcome analysis for the effectiveness of XR-NTX vs. placebo, and XR-NTX vs. O-NTX is described in Section 9.1. The secondary outcome analyses are described in Section 9.2.

In the case of missing assessments, such analysis can include these participants provided that prerandomisation values are available for the respective scales. The analysis presumes that the drop-out mechanism is missing at random (MAR). We will examine the scope for using multiple imputation (MI) to generate complete data records as a means of achieving greater efficiency and reduced missing data bias. We will also include as covariates in both model and MI any variables found to be associated with drop-out.

The significance level will be 2.5% (two-sided) for the primary outcome analysis and 5% (two-sided) for secondary outcome analysis. Group difference estimates and associated confidence intervals will be reported. The trial statistician will remain blind whenever possible until the main analyses have been completed.

Loss to follow-up, departures from randomized treatment and the prevalence of serious adverse events will be reported at 12, 16, 24 and 36 weeks post randomization.

## 13. Trial Steering Committee

A Trial Steering Committee (TSC) and a Data Monitoring Committee (DMC) will operate independently from the Trial Management Group (TMG), the study funder (NIHR/HTA), and the Cosponsors (King's College London & South London and Maudsley NHS Foundation Trust). The operation of each group is summarised as follows:

The TSC's key purpose will be to ensure the overall integrity of the study; monitoring its progress; investigating any serious adverse events; and taking account of regular reports from the DMC and

TMG. Ultimate responsibility for any decision required on the trial's continuation will lie with the TSC. The Committee will consist of an independent Chair (Professor of Addiction Psychiatry or Psychology), and four other members:

- A Patient and Public Involvement representative;
- A Senior Manager from Public Health England;
- An NHS addiction service commissioner;
- A healthcare treatment provider;

There will also be three overseas members: Professors [name] (University of St. Petersburg, [name] (University of New York) and [name] (University of California Los Angeles). These external members have been costed to attend the London centre for one visit each and we will invite their participation at other meetings via teleconference.

The TSC's membership will be approved by the Sponsor, and will reflect all relevant disciplines. TSC meetings will be attended by the Chief Investigator (JS), Lead Investigator (JM), at least one PI (ED, MK or SM), KCTU Manager (CM), Trial Statistician (JH) and Trial Manager (TBA, secretary to the TSC). The co-sponsor representative (TBA) will be invited to observe each meeting. The TSC is expected to meet six times across the study (or more often, if determined by the Chair.

## 14. Data Monitoring Committee

The DMC's key purpose will be to monitor the trial data to ensure that it is being implemented in accordance with the highest standards of patient safety and ethical conduct. Throughout the trial, the Committee will monitor data on recruitment, adverse events, emerging external evidence, sample characteristics and primary outcomes and make recommendations if any interim analysis is required.

The DMC will consist of an independent Chair (a senior clinician with expertise in addiction pharmacotherapy trials) and three other members: a university based trials statistician not involved in the study; a treatment provider; and a Patient and Public Involvement representative.

The DMC's membership will be approved by the Sponsor. DMC meetings will be attended by the Chief Investigator (JS), Lead Investigator (JM), KCTU Manager (CM), Trial Statistician (JH) and Trial Manager (TBA, secretary to the DMC). The DMC will meet six times on the same Study Month schedule as the TSC.

## 15. Trial Management Group (TMG)

The TMG will be responsible for the trial's day-to-day running and management. Chaired by the Chief Investigator (JS) or the Lead Investigator (JM), the membership will include: all investigators; the KCTU Manager (CM); Trial Statistician (JH); Health Economist (SB); Trial Manager (TBA, Secretary to the TMG); Data Manager (JK); and a Patient and Public Involvement representative. The TMG will oversee the development and operation of the study, monitor and maintain recruitment rates, and devise any necessary workarounds that may arise in patient management or the conduct of the trial, ensure that all required financial, insurance and indemnity arrangements are instigated, organise site agreements between each of the three clinical centres and the Study Office and draw up the study publication policy and strategy. The TMG will be divided into three work-streams to oversee: the development of the study protocol and assessments; the trial database; and writing papers. These sub-committees will be appointed by the full TMG and will meet as necessary.

### 16. Direct Access to Source Data and Documents

The Investigator(s) will permit trial-related monitoring, audits, REC review, and regulatory inspections by providing the Co-Sponsor(s), Regulators and REC direct access to source data and other documents (eg patients' case sheets, blood test reports, histology reports etc).

## 17. Ethics & Regulatory Approvals

The trial will be conducted in compliance with the principles of the Declaration of Helsinki (1996), the principles of GCP and in accordance with all applicable regulatory requirements including but not limited to the Research Governance Framework and the Medicines for Human Use (Clinical Trial) Regulations 2004, as amended in 2006 and any subsequent amendments.

This protocol and related documents will be submitted for review to London Dulwich Research Ethics Committee (REC), and to the Medicines and Healthcare products Regulatory Agency (MHRA) for Clinical Trial Authorisation.

The Chief Investigator will submit a final report at conclusion of the trial to the KHP-CTO (on behalf of the Co-sponsor), the REC and the MHRA within the timelines defined in the Regulations.

In relation to the study's registration and adoption: an MHRA Clinical Trial Authorisation application will be made. NEAT has been registered with EudraCT and will be registered with clinicaltrials.gov, a publicly accessible database, before participant recruitment. The Co-sponsors will be King's College London & South London and Maudsley NHS Foundation Trust and the research team will apply for adoption by the Mental Health Research Network.

## 18. Quality Assurance

Monitoring of this trial will be to ensure compliance with Good Clinical Practice and scientific integrity will be managed and oversight retained, by the KHP-CTO Quality Team.

The trial will incorporate a range of data management quality assurance functions. As the data are entered online, the Data Manager will log any queries generated and feed these back to the centre research workers in a timely manner. Maintaining a single point of contact between each centre and the KCTU, the KHP-CTO CRA will conduct regular monitoring visits at each centre. Any necessary alterations to entered data will be indicated clearly with an audit trail from the original point of data entry, to ensure that any such amendments, and the reasons for them, can be inspected and tracked. KHPCTO will undertake, on behalf of the Sponsor, independent administrative audits of the trial master file and monitoring at all sites and pharmacies periodically during the trial to ensure compliance with the Medicines for Human Use (Clinical Trials) Regulations 2004 and its subsequent amendments.

### 18.1 Quality assurance of the psychological intervention

The following procedures will ensure and document the integrity and fidelity of the behavioural interventions.

- Preparation of manuals for the behaviour therapy to incentivize clinic attendance and the mapping-based care planning and task-setting case management model. These materials will be web-accessible as part of the publication of study reports;
- Standardized delivery of these interventions achieved through a staff training programme organized during the preparatory phase, and supplemented by routine clinical supervision;
- A Session Record form which will be completed by the patient and therapist to provide a summary of the methods used in each session; and

- With consent from the patient, 12 weekly key work sessions (including those focusing on mapping, task setting and relapse prevention) will be audio recorded.
- These digital files will be stored securely as part of the study record.
- As these are collected, one of the four session recordings in each of the 3 months will be randomly selected and rated independently for detailed fidelity analysis.

Adapted from a protocol the NEAT team has developed for a behaviour therapy trial in opioid agonist maintenance therapy, these will be rated for protocol adherence by an independent clinician. Any departure from the protocol in terms of content or style of interaction will result in further supervision.

## 19. Data Handling

The Chief Investigator will act as custodian for the trial data. The following guidelines will be strictly adhered to:

Patient data will be anonymised.

- All anonymised data will be stored on a password protected computer.
- All trial data will be stored in line with the Medicines for Human Use (Clinical Trials) Amended Regulations 2006 and the Data Protection Act and archived in line with the Medicines for Human Use (Clinical Trials) Amended Regulations 2006 as defined in the KHP-CTO Archiving SOP.

Centre PIs will ensure that all personnel are familiar and comply with these guidelines. Data management procedures for the trial will be developed and overseen by the King's Clinical Trials Unit.

### 19.1 Data collection

Baseline data will be collected and entered by researchers in each study site prior to randomization. Each participant will be assigned a unique trial ID number via the InferMed MACRO eCRF system hosted at the KCTU at the start of the assessment process. This number will be written on all clinical assessment forms, datasheets and databases used to record participant data. Trial data will be first entered on to paper source datasheets provided to each centre during the preparation phase. The research team will endeavour to minimise the use of paper at all times. A hard copy of a record sheet linking patient identity, contact details and trial ID number (including medication pack number) for all participants will be kept at each site. This will be placed securely in a locked filing cabinet separate from datasheets. All data will be kept secure at all times and maintained in accordance with the requirements of the Data Protection Act and archived locally according to the KHP-CTO Archiving SOP and the host institution's additional procedures.

## 20. Data Management

All baseline and follow-up data will be entered on the online InferMed MACRO electronic data capture (EDC) system (infermed.com). This system is regulatory compliant (GCP, 21CRF11, and the EC Clinical Trial Directive). An electronic case report form (eCRF) using the MACRO EDC will be programmed by the KCTU in collaboration with the Trial Manager (TBA), Trial Statistician (JH) and Health Economist (SB), and hosted on a dedicated secure server within KCL.

The eCRF system will have full audit trail, data discrepancy functionality, database lock functionality, and supports real time data cleaning and reporting. The KCTU will provide training, essential documentation, and user support to the study centres, and on-site audit and monitoring.

A detailed Standard Operating Procedure will cover data recording, online entry, checking, central backup and storage. A regularly updated coding manual will be developed to accompany the study database. The Trial Manager will provide usernames and passwords to any new researchers. Only those authorised by the Trial Manager will be able to use the system.

